5.1. Disposition

Disposition will be summarised for all enrolled patients by treatment arm and overall. The number and percentage of patients who have been enrolled, have been treated (i.e., Safety analysis set), have completed the study treatment, have completed the study, have discontinued from the study treatment, have discontinued from the study, as well as the primary reason for the study treatment discontinuation and the study discontinuation will be tabulated.

Additionally, a summary of the analysis sets will be provided to include the number and percentage of patients in each analysis set by treatment arm and overall. A summary of the analysis sets by treatment arm and country will also be presented. Patient disposition, analysis sets and screen failures will be presented in a listing.

5.2. Protocol Deviations

Protocol deviations will be recorded within the PPD Clinical Trial Management System (CTMS) and undergo cross-functional team review prior to database lock. In addition, protocol deviation classification (i.e., significant vs. non-significant) as determined by sponsor prior to database lock will be documented in CTMS. Protocol Deviations related with COVID-19 will be assessed and reported accordingly.

The number and percentage of patients with significant protocol deviations will be summarised by CTMS activity subtype, treatment arm and overall using the Safety analysis set. Individual patient protocol deviations, both significant and non-significant, will be presented in a data listing using the Enrolled set.

6. Demographics and Baseline Characteristics

6.1. Demographics

Baseline demographics will be summarised by treatment arm and overall, for all patients in the Safety analysis set. Baseline demographic data to be evaluated will include age, sex, geographical origin, fertility status, height (cm), weight (kg) and body mass index (BMI) (kg/m^2). Descriptive statistics will be presented for age (18-75 years inclusive), height and weight. Sex, geographic origin, and fertility status will be summarised categorically. Demographic and baseline characteristics data will be listed for all patients in the Safety analysis set.

6.2. Medical and Surgical History

Medical and surgical history will be summarised by treatment arm and overall, for all patients in the safety analysis set. Medical and surgical history data will be summarised by Medical Dictionary for Regulatory Activities (MedDRA) system organ class (SOC) and preferred term (PT). The dictionary version used for reporting the study will be described in the relevant table and listing footnotes. Percentages will be calculated based on the number of patients in the Safety Analysis Set. Medical history will be coded using MedDRA Version 28.0.

Medical history data including specific details will be presented in a listing.

6.3. Inclusion and Exclusion Criteria

The details of Inclusion and Exclusion criteria are listed in Section 7.2.2 and 7.2.3 of the protocol. All inclusion/exclusion criteria related information for enrolled patients will be presented in a data listing. The listing will include those failed inclusion/exclusion criteria.

7. Treatments and Medications

7.1. Prior and Concomitant Medications

Medications will be coded using the World Health Organization (WHO) Drug B-3 Dictionary dated March, 2025. The WHO Drug Dictionary version used for reporting the study will be described in the relevant table and listing footnotes. If the medication start or end date is missing, it will be imputed before summary as described in [Appendix 1](#). If the start date of a medication is completely missing and the end date is within 14 days before the dosing of study drug on Day 1, it will be counted as a prior medication. If the start date of a medication is completely missing and the end date is after the dosing of study drug on Day 1 it will be counted as both a prior and concomitant medication. If the start date of a medication is on or after the dose of study drug on Day 1 and the end date of the medication is completely missing, it will be counted as a concomitant medication. Prior and concomitant medications will be summarised and listed based on the Safety analysis set.

7.1.1. Prior Medications

Prior medications are defined as those medications taken by a patient within 14 days prior to the first intake of study drug. The total number of prior medications will be summarised. The number and percentage of patients with at least one prior medication will be summarised overall and by Anatomical Therapeutic Chemical (ATC) level 4 term and PT. Prior medications will be presented by treatment and overall using the Safety Analysis Set. Medications will be listed in a descending order by ATC level 4 category based on the Overall of all treatment arms. Within each ATC level 4 category, PTs will be listed in an alphabetical order.

7.1.2. Concomitant Medications

Concomitant medications are defined as those non-study medications taken on or after the first day of study drug dose through 14 days after the last dose of study drug. The total number of concomitant medications will be summarised in a table. The number and percentage of patients with at least one concomitant medication will be summarised by ATC level 4 term and PT. Concomitant medications will be presented by treatment and overall using the safety analysis set. Medications will be listed in a descending order by ATC level 4 category based on the Overall of all treatment arms. Within each ATC level 4 category, PTs will be listed in an alphabetical order.

7.2. Study Drug Administration

Onsite study drug administration will be listed for each patient in the Safety analysis set.

7.3. Study Treatments

7.3.1. Extent of Exposure

Treatment Exposure will be displayed by the single dose (Day 1 to Day 14) and 12-week (Day 15 to Day 112) treatment periods. For single dosing period, number of patients who received the single dose will be presented based on the Safety Analysis Set. Duration of 12-week treatment period exposure is defined as the total number of days a patient is exposed to the study drug during the 12-week treatment period. Duration of 12-week treatment period exposure will be presented as the total number of days from the first dose date and time in the 12-week treatment period to the last dose date and time (date of last known study drug administration minus the date and time of first dose in the 12-week treatment period + 1) as recorded on the End of Treatment electronic case report form (eCRF). If the last dose date and time on the End of Treatment page is missing, then the last dose date and time recorded on the A3907 Administration page of eCRF will be used. Duration of 12-week treatment period will be categorized into time intervals and frequency counts and percentages will be presented for the number (%) of patients in each interval. The time intervals will be grouped into the following categories: 1 to 14 days, > 14 to ≤ 28 days, > 28 to ≤ 42 days, > 42 to ≤ 70 days, > 70 to ≤ 98 days, and > 98 days. Duration of exposure will also be summarised using descriptive statistics. For 12-week treatment period summary, percentages will be computed from the number of patients in the Safety Analysis Set who actively entered 12-Week treatment period. All doses will be included in the listing based on the Safety Analysis Set.

7.3.2. Treatment Compliance

Compliance will be calculated as: $\text{Treatment Compliance} = 100 \times ([\text{Number of study drug dispensed} - \text{number of study drug returned}] \text{ across the 12-week treatment period} / \text{number of study drug that should be taken})$. The total number of tablets actually taken is the total number of tablets recorded as taken based on the eCRF (number of tablets dispensed minus returned) summed over the 12-week treatment period. If the number of tablets returned is confirmed as missing and the study drug is confirmed as not been returned, the derivation will not be done. Treatment compliance overall and by treatment will be summarised using descriptive statistics and following categories: < 80%, ≥ 80%-≤ 100%, > 100%-≤ 120% and > 120%. A listing of Study Drug Compliance will be presented based on the number of patients in Safety Analysis Set who actively entered 12-Week treatment period.

8. Secondary and Exploratory Analysis

8.1. Pharmacokinetic Analysis

PK analyses will be described in separate analysis plans, and results will be reported outside the Clinical Study Report for the study.

8.2. Pharmacodynamic analyses

Secondary and exploratory PD variables (bile acids, C4, FGF-19, autotaxin, ProC3, hsCRP, MMP7, MMP9, ELF score, and CA 19-9) will be analyzed descriptively for categorical and continuous data, as applicable. For continuous data, the relative and absolute change from baseline 1 at each post-baseline visit will be analyzed in addition to the actual values. 2-sided 95% CI of the mean for relative and absolute change from baseline 1, and actual values will be

presented along with descriptive statistics. Similarly, summary tables presenting relative and absolute change from baseline 2 for the 12-week treatment period will be presented. For categorical data, shift tables or frequency and percentages of patients will be presented as appropriate.

8.2.1. Bile Acids

Individual and total serum and urine bile acids will be presented. The relative and absolute change from baseline 1 in individual and total serum bile acids parameters will be presented at visits in [Table 1](#). For serum bile acid parameters, baseline 1 is defined as the average of all Screening results and results on the day of the planned single dose if both results are available. Otherwise, baseline 1 will be defined as the last non-missing assessment prior to the study drug administration of planned single dose. Similarly, the relative and absolute change from baseline 1 in urine samples for individual and total bile acids parameters will be presented at visits in [Table 2](#). For urine bile acid parameters, baseline 1 is defined as the last non-missing assessment of that parameter prior to the study drug administration of planned single dose.

The following bile acid parameters will be summarised in two units ($\mu\text{g/mL}$ or $\mu\text{mol/L}$) if applicable:

- Observed individual serum bile acids
- Observed total serum bile acids (both central lab data and specialized vendor data will be presented)
- Calculated total serum bile acids without all UDCA bile acids, which is the sum of all individual serum bile acids excluding all UDCAs (UDCA, GUDCA, TUDCA)
- Calculated conjugated serum bile acids (GCA, GLCA, GDCA, GCDCA, GUDCA, TCA, TCDCA, TDCA, TLCA, TUDCA)
- Calculated unconjugated serum bile acids (CA, LCA, DCA, CDCA, UDCA)
- Observed individual urine bile acids
- Observed total urine bile acids
- Calculated total urine bile acids without all UDCA bile acids, which is the sum of all individual urine bile acids excluding all UDCAs (UDCA, GUDCA, UDCA-S, GUDCA-S)
- Calculated conjugated urine bile acids (GCA, GLCA, GDCA, GCDCA, GUDCA)
- Calculated unconjugated urine bile acids (CA, LCA, DCA, CDCA, UDCA)
- Calculated conjugated urine sulfated bile acids (GCA-S, GLCA-S, GDCA-S, GCDCA-S, GUDCA-S)
- Calculated unconjugated urine sulfated bile acids (CA-S, LCA-S, DCA-S, CDCA-S, UDCA-S)

Summary tables presenting the relative and absolute change from baseline 1 in urine bile acids amount will be presented at visits in [Table 2](#). Urine bile acids amount will be calculated as follows:

Urine bile acid amount (μg) = Urine bile acid concentration under unit $\mu\text{g/mL}$ \times [(Urine weight (g)) / (Urine density)]. The density for Urine is 1.005 g/mL.

Urine bile acid amount (μmol) = Urine bile acid concentration under unit $\mu\text{mol/L}$ \times [(Urine weight (g)) / (Urine density)] $\times 0.001$. The density for Urine is 1.005 g/mL.

The following urine bile acid amount parameters will be summarised in two units (μg and μmol):

- Individual Urine Bile Acid Amount
- Total Urine Bile Acid Amount
- Total Urine Bile Acid Amount without all UDCAs
- Conjugated Urine Bile Acids Amount
- Conjugated Urine Sulfated Bile Acids Amount
- Unconjugated Urine Bile Acids Amount
- Unconjugated Urine Sulfated Bile Acids Amount

Similar summary tables presenting relative and absolute change from baseline 2 for the 12-week treatment period will be presented for all above bile acid parameters for patients in the PD analysis set who actively entered the 12-Week treatment period. Baseline 2 for the 12-week treatment period is defined as the last non-missing value of the assessment prior to the 12-week treatment period (V3).

A listing of bile acid levels will be presented for the PD analysis set. For urine bile acid levels, urine sample collection duration will be included in the listing. It will be calculated under unit hour as follows:

Urine sample collection duration = (Collection End Datetime – Collection Start Datetime) / 3600.

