- ^h Plasma PK samples for Arm 1+2 will be obtained on Day 0 (Visit 2) and Day 98 (Visit 7) pre-dose and at 0.5, 1, 1.5, 2, 4, 6, 8 and 10 hours post-dose (\pm 5 minutes). Plasma PK samples for Arm 3+4 will be obtained on Day 0 (Visit 2) pre-dose and at 0.5, 1, 1.5, 2, 4, 6, 8, 12 and 24 hours post-dose (\pm 5 minutes). The 12-hour sample collection will be obtained post administration of the first BID dose, but before administration of the second BID dose, and the 24-hour sample collection will be obtained before study drug administration the following morning. On Day 98 (Visit 7), PK samples for Arm 3+4 will be obtained pre-dose and at 0.5, 1, 1.5, 2, 4, 6, 8, and 10 hours post-dose (\pm 5 minutes). The post-dose sample collections will be obtained post administration of the first BID dose. Sampling timepoints at Day 98 (Visit 7) may be adjusted based on observed data from Day 0 (Visit 2) without changing the total number of blood samples. For Visits 3 to 6 (inclusive), PK will be collected once pre-dose, and once for Visit 8. In the case of hepatic adverse events and/or hepatic decompensation, a PK sample should be collected as close to the onset of the event as possible. In the case of hepatic adverse events and/or hepatic decompensation, a PK sample should be collected as close to the onset of the event as possible.
- ⁱ Metabolites (MIST) samples will be obtained on Day 0 (Visit 2) and Day 98 (Visit 7) pre-dose, 2, 4, 8 and 12 hours post dose (\pm 5 minutes). Sampling timepoints may be adjusted based on observed data from Day 0 (Visit 2) without changing the total number of blood samples.
- ^j Serum bile acid levels will be obtained once per applicable visit, pre-dose. Serum bile acid levels will be obtained once on Visit 8.
- ^k Serum samples for C4 and FGF-19 will be obtained once per applicable visit, pre-dose.
- ^l Biomarkers include autotaxin, ProC3, hsCRP, MMP7, MMP9, ELF score, AFP and CA 19-9. Serum samples will be obtained once per applicable visit—pre-dose. Serum samples will be obtained once on Visit 8.
- ^m Urine will be collected by the patient for the 24-hour period prior to study visit.

- ⁿ The safety laboratory parameters to be assessed are presented in [Table 2](#).
- ^o Confirmatory FSH for women of WONCBP upon Screening.
- ^p Serum pregnancy test for all women upon Screening.

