9.5 Pharmacodynamic Assessments

9.5.1 Bile Acids

Blood samples for analysis of individual and total serum bile acids will be drawn at all study visits from Visit 1 through Visit 8.

Urine samples for analysis of individual and total bile acids will be collected by the patient during the 24-hour period prior to Visits 2, 3, 5, 7, and 8. Instructions for the urine collection can be found in the laboratory manual.

For any visit at which a bile acid sample result is unreportable, an additional unscheduled visit for a repeat sample collection may be scheduled. Samples will be handled, stored, and transported to a central laboratory per instructions in the laboratory manual.

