Biweekly score for pruritus NRS and/or fatigue NRS, sleep disturbance NRS, mood Likert scale	
12-week treatment period biweekly (14 days) score is calculated by averaging the weekly scores in the two weeks of the biweekly period.
 
It can only be calculated if both weeks can be calculated. If weekly score is not available, the post-single dosing biweekly score is calculated by averaging all the daily scores if at least 7 daily scores available. Otherwise, it is considered as missing.

Variables	Formula
Monthly score for pruritus NRS and/or fatigue NRS, sleep disturbance NRS, mood Likert scale	The 12-week treatment period monthly (28 days) score is calculated by averaging 4 weekly scores within the 4-week interval. The monthly score can only be calculated if at least 3 of 4 weekly scores within the 4-week interval can be calculated.
Change from baseline for pruritus NRS and/or fatigue NRS, sleep disturbance NRS, mood Likert scale	The weekly, biweekly, and monthly score change from baseline is calculated by subtracting the baseline score from the weekly, biweekly and monthly score.
Urine Sample Collection	
Duration of urine sample collection (hours)	$(\text{Collection End Datetime} - \text{Collection Start Datetime}) / 3600.$

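### Urine bile acid amount is not scaled to 24 hours: the SAP derives each collection's actual duration but only lists it, so off-time collections are neither corrected nor screened

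*SAP*

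**What the plan says.** **Collection.** Footnote m to the schedule (Protocol 7.1.2) reads: "Urine will be collected by the patient for the 24-hour period prior to study visit". Protocol 9.5.1 repeats the 24-hour requirement and names Visits 2, 3, 5, 7 and 8.

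**Amount.** SAP 8.2.1 multiplies concentration by urine weight over density, in µg and in µmol, with a fixed constant: "The density for Urine is 1.005 g/mL". The formula has no time term. On reporting it says: "Summary tables presenting the relative and absolute change from baseline 1 in urine bile acids amount will be presented at visits in" its Table 2. The same summaries are repeated against baseline 2, the value before the 12-week period. SAP 8.2 adds two-sided 95% confidence intervals for the mean relative and absolute change in the continuous PD variables.

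**Duration.** SAP 8.2.1 defines it: "Urine sample collection duration = (Collection End Datetime – Collection Start Datetime) / 3600". Appendix 3 repeats the formula. The only stated use is this: "For urine bile acid levels, urine sample collection duration will be included in the listing".

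**What is absent.** Neither document scales the amount to 24 h, sets an acceptable duration, excludes short or long collections, or plans a sensitivity analysis for them. The PD analysis set (SAP 4.3.5) needs only one evaluable PD marker. Urine creatinine is not among the listed laboratory parameters (Protocol Table 2, SAP Appendix 2), so it cannot serve as a completeness check.

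**The concern.** An amount without a time base is comparable between visits only if every collection lasted equally long. These are home collections timed by patients, and the sponsor evidently expects some variation, since it derives the actual duration. The change summaries then ignore it.

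The measure matters to this trial. Change in urine bile acids to Week 12 is part of a secondary endpoint. Loss of bile acids in urine is one of the effects expected from a systemically available inhibitor (Protocol 5.3). The direction is still open: Protocol 5.2.3 reports that urinary bile acids rose in mice, while total urinary excretion in the first-in-human study was lower than on placebo at all doses.

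The design gives little protection. Each arm has six patients and there is no reference treatment. Urine baseline 1 is a single pre-dose collection, whereas serum baseline 1 averages Screening and dosing-day results when both exist. One off-time urine baseline therefore enters that patient's change from baseline 1 at every later visit.

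**Working it through.** The documents give no figure to reproduce here and no information on how far durations depart from 24 h. All durations and duration SDs below are assumptions.

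**1. Units.** For 1500 g of urine, volume = 1500 / 1.005 = 1492.5 mL. At 10 µg/mL the amount is 14,925 µg. At 20 µmol/L it is 20 × 1492.5 × 0.001 = 29.85 µmol. Both formulas are dimensionally correct and give mass per collection.

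**2. One patient, no true change.** With a constant excretion rate r, amount = r × T, so the apparent relative change is T2/T1 − 1. The scaled amount is r × T × 24/T = 24r at any T, so its change is 0%.

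| Assumed T1, T2 (h) | Unscaled change | Scaled change |
|---|---|---|
| 24, 22 | −8.3% | 0% |
| 24, 20 | −16.7% | 0% |
| 20, 24 | +20.0% | 0% |
| 22, 26 | 26/22 − 1 = +18.2% | 0% |

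One patient at +18.2% moves a six-patient mean by 18.2 / 6 = 3.0 percentage points.

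**3. Random timing error.** Let durations at both visits have mean 24 h and SD s. To first order, the SD of one patient's apparent change is √2 × s/24, and the SD of the arm mean is that divided by √6.

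- s = 2 h: √2 × 2/24 = 11.8 points per patient; 11.8/√6 = 4.8 for the arm mean.
- s = 4 h: √2 × 4/24 = 23.6 points per patient; 23.6/√6 = 9.6 for the arm mean.

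A simulation (200,000 runs, six patients, t-based 95% intervals) agrees:

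| Duration SD | Mean bias | SD, one patient | SD, arm mean | Arm mean off by >10 points | 95% CI excludes 0 |
|---|---|---|---|---|---|
| 2 h | +0.7% | 12.0 | 4.9 | 4.5% | 5.0% |
| 4 h | +3.1% | 25.8 | 10.5 | 33.8% | 4.9% |

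The interval keeps its nominal error rate, so random timing error shows as lost precision.

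**4. Share of total variation.** With an assumed within-patient CV of 20% in excretion itself, the SD of the log change is 0.280 without timing error, 0.304 with s = 2 h and 0.372 with s = 4 h. The increases are 0.304/0.280 − 1 = 9% and 0.372/0.280 − 1 = 33%. With a CV of 40% the values are 0.545, 0.558 and 0.597, increases of 2% and 10%.

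**5. Systematic shift.** If Week 12 collections are on average shorter than baseline collections, the mean is biased:

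| Assumed mean shortfall | Mean change | CI excludes 0, SD 1 h | CI excludes 0, SD 2 h |
|---|---|---|---|
| 2 h | about −8% | 79% | 30% |
| 4 h | about −16% | 100% | 79% |

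These runs contain timing error only. Biological variation would lower the exclusion rates but would not remove the bias.

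**The case against.** A reader might infer that the amount is computed from an undefined collection, and that timing error will therefore appear as a drug effect on the secondary endpoint. The documents do not support this.

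- The protocol fixes the collection at 24 h, so the amount is nominally a 24-hour amount. The gap concerns departures from 24 h.
- Random departures barely shift the mean and leave interval coverage nominal. An arm-level false effect needs a systematic difference between visits, or chance in a small arm. Nothing in the documents suggests that Week 12 collections will be systematically shorter or longer.
- The endpoint is worded as bile acid levels. SAP 8.2.1 also summarises urine concentrations, which use neither weight nor duration, and serum values are untouched. Only the amount tables are exposed.
- The analysis is descriptive, with no test or decision threshold. Median and range are reported, and the listing lets a reader find odd durations.
- Collection instructions are in the laboratory manual, which is not among the documents and may contain acceptance rules. Protocol 9.5.1 allows repeat sampling, but only for an unreportable result.

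Scaling has limits too. It assumes a roughly constant excretion rate, and Protocol 5.4 reports a post-prandial rise in serum bile acids. A wrongly recorded time would distort a complete collection. Missed voids stay uncorrected.

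These arguments narrow the point but do not remove it. A listing does not adjust a mean, and a rule in the laboratory manual would not change the SAP formula.

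**Conclusion.** The point holds in a limited form. SAP 8.2.1 compares mass per collection between visits while the recorded duration goes unused, and neither document corrects or screens departures from 24 h. Any difference in duration enters a patient's apparent change in full, if excretion is roughly constant. For an assumed duration SD of 2 to 4 h, this adds about 5 to 10 percentage points of SD to a six-patient arm mean. That is mainly avoidable noise. A systematic shift would bias the mean (about −8% for an assumed 2 h shortfall), and without a control arm it could not be told apart from a change on treatment. The omission is certain from the text. Its size depends on durations that the documents do not give. It is a worthwhile, inexpensive improvement to the amount tables and does not threaten the endpoint as a whole.

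**What to change.** In SAP 8.2.1:

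1. Define amount per 24 h = amount × 24 / recorded collection duration (h), and use it for the amount summaries of change from baseline 1 and from baseline 2.
2. Keep the unscaled amount as a supportive summary, and as the fallback when a start or end time is missing.
3. Add a sensitivity summary that excludes collections outside a duration window. The documents offer no basis for particular limits, so the sponsor should choose and pre-specify them.
4. State the limits of scaling: it assumes a roughly constant excretion rate, relies on accurate recorded times, and does not correct missed voids.

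The cost is a short SAP edit, one derived variable and some additional tables. Duration is already derived, so no new data are needed.
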